#### **What is the cause of these symptoms?**

Miglustat stops the intestinal enzymes that break down disaccharides (mainly sucrose, maltose, and to a lesser amount lactose) from working. These disaccharides (sugars) are not digested and absorbed properly, and stay in the gut. This can cause diarrhea. These sugars are also “food” for the bacteria in your gut and are fermented, producing gas. This also means your body doesn’t absorb these sugars and you aren’t getting the calories from them.

#### **What can I do to minimize these symptoms?**

- Take miglustat separately from meals (e.g. 2 hours before or after meals)
- Start dietary changes at least 3 days (up to 2 weeks) before you start taking miglustat
- Consider gradually increasing your dose (as recommended by your doctor)
- Eat a diet low in disaccharides (sucrose, maltose, and to a lesser extent lactose)

\*\*Miglustat absorption is not affected if you have diarrhea as it is rapidly absorbed in the gut after it is taken

#### **What is a disaccharide?**

Disaccharides are two monosaccharides (single sugars) joined together.

Examples of disaccharides:

- Sucrose (table sugar) is made up of glucose and fructose joined together.
- Maltose is glucose and glucose joined together.
- Lactose (or milk sugar) is a galactose and glucose joined together.

#### **What is a low disaccharide diet?**

It is a diet low in sucrose, maltose, and lactose.

Reduce disaccharides to <5g per meal. Look at the sugars on the nutrition label and the ingredient list to get an idea of how much disaccharide is in a food.

Avoid eating foods high in disaccharides (sucrose and maltose)

**Desserts:** cookies/biscuits, cakes, pies, puddings, custard, ice cream, sweetened yogurt

**Certain fruits:** bananas, dates, peaches, apricots, pineapples, mangos, tangerines, dried fruits

**Additives/condiments:** molasses, sugar, chocolate, jam, marmalade, honey, Nutella, sugar-based syrup

Avoid high-carbohydrate drinks such as naturally sweetened soft-drinks, sweetened fruit juices, and alcohol-containing drinks (beer/wine). Fructose containing food and fruit drinks, and artificially sweetened soft drinks may be consumed.

Reduce dairy intake (milk, cream, yogurt, cream cheese)

-Lactose-free and soy based products can be used to replace milk and yogurt

-Unsweetened and/or soy based yogurts allowed

-Ensure you are meeting your calcium and Vitamin D requirements from diet and/or supplements

Reduce intake of starchy foods as the body naturally produces maltose (a disaccharide) as it digests foods such as bread, breakfast cereals, legumes, potatoes, corn, rice, beans, pasta and other grains.

- Avoid large servings starchy foods at one time
- Spread out your intake of starchy foods over the day

If GI symptoms continue, intake of starchy foods may need to be more severely reduced, and then slowly re-introduced one-by-one over several weeks/months.

### **Will I always have to be this strict with my diet?**

As your gut adapts to miglustat therapy and symptoms improve, you may be able to slowly re-introduce foods back into the diet. This would be done slowly and would be based on your tolerance.

### **What about eating out/special occasions?**

For parties or social occasions where it is hard to avoid high disaccharide foods (e.g. birthday cake) consider taking Imodium. Imodium increases the amount of time that food remains in the gut, improving carbohydrate digestion and absorption. This may limit diarrhea and abdominal pain.

### **Will I lose weight?**

Ideally we do not want you to lose weight on miglustat (assuming you are at a healthy weight to start with). It is very important that you maintain an adequate calorie intake while taking miglustat.

If you are getting less calories from carbohydrates, then you will need to get these calories from protein and fats.

Protein Sources: non-breaded meat/fish, eggs, tofu, nuts and seeds

Fat Sources: oils, margarine, and avocado

You may need to snack more often.

Monitor your weight regularly (e.g. at least once a month). Let your doctor, nurse or dietitian know if you are losing weight.

### **Can probiotics help with my symptoms?**

Probiotics (e.g. live cultures in yogurt) may help. There has not been a lot of research done about this. Taking probiotics, which deliver helpful bacteria to the gut, might help with symptoms while on miglustat. Probiotics that break down disaccharides seem to be helpful. One study showed Tilactase and Lactobacillus reuteri improved symptoms related to eating lactose people who were lactose intolerant.

## 13.2 Appendix 2: Unified Batten Disease Rating Scale

Page 1 of 8  
(1)

### NEURONAL CEROID LIPOFUSCINOSIS (NCL) STUDY GROUP UNIFIED BATTEN DISEASE RATING SCALE

All items must be completed. Use U if information is Unavailable or Not Applicable.

SUBJECT NO.    INITIALS (First, Middle, Last)    SITE NO.

DATE INFO OBTAINED (mm/dd/yyyy)

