24. GENERALIZED TONIC/CLONIC  
SEIZURES: POST-ICTAL PERIOD

24.

0 = none/not-applicable  
1 = less than 1 minute  
2 = more than 1 and up to 10 minutes  
3 = more than 10 minutes and up to 1 hour  
4 = more than 1 hour and up to 3 hours  
5 = more than 3 hours

25. ATONIC SEIZURES:  
AVERAGE FREQUENCY

25.

0 = none  
1 = fewer than one per 6 months  
2 = more than one per 6 months and up to one per 3 months  
3 = more than one per 3 months and up to one per month  
4 = more than one per month and up to one per week  
5 = more than one per week and up to one per day  
6 = more than one per day

26. MYOCLONIC SEIZURES:  
AVERAGE FREQUENCY

26.

0 = none  
1 = fewer than one per 6 months  
2 = more than one per 6 months and up to one per 3 months  
3 = more than one per 3 months and up to one per month  
4 = more than one per month and up to one per week  
5 = more than one per week and up to one per day  
6 = more than one per day

SUBJECT NUMBER 

--	--	--

INITIALS (First, Middle, Last) 

--	--	--

Page 4 of 8

(1)

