33. HOSPITALIZATION REQUIRED  
FOR TREATMENT OF SEIZURES  
(due to any seizure type/past 6 months)

33.

0 = none/not applicable  
1 = once  
2 = more than once

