52. SCHOOL

52.

0 = normal ability in mainstream classroom  
1 = marginal ability in mainstream classroom  
2 = requires special needs classroom  
3 = unable to attend special needs classroom

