**All items must be completed. Use U if information is Unavailable or Not Applicable.**

**VI. NCL HISTORY (TO BE COMPLETED BY FIRST RATER)**

**Instructions:** For each symptom, ask if child has experienced the symptom and if so, obtain approximate age of onset in years and months (e.g., age 4 1 / 2 should be coded as 04 for years and 06 for months). For each symptom reported as experienced, the rater should rank in order of onset beginning with 1. If child has not experienced symptom, code as U for not applicable.

Symptom	Experienced Symptom 0 = No, 1 = Yes	Onset Age		Rater Ranking Order of Onset (1 = first, 8 = last)
		Years	Months	
58a. Loss of vision	58a. 	58a1.  	58a2.  	58a3. 
58b. Motor difficulties	58b. 	58b1.  	58b2.  	58b3. 
58c. Cognitive difficulties	58c. 	58c1.  	58c2.  	58c3. 
58d. Behavioral difficulties	58d. 	58d1.  	58d2.  	58d3. 
58e. Seizures	58e. 	58e1.  	58e2.  	58e3. 
58f. Weight loss/feeding difficulties	58f. 	58f1.  	58f2.  	58f3. 
58g. Sleep disturbance	58g. 	58g1.  	58g2.  	58g3. 
58h. Other (Specify) _____	58h. 	58h1.  	58h2.  	58h3. 
<hr/> <hr/>				

**59. COMMENTS** \_\_\_\_\_

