**Table 2. UBDRS Domains/Subscales and Analysis Methods**

Domain	Contributing Questions	Method of Summarization	Imputation Rules
Physical Assessment	1, 1A, 2, 3, 4A, 4B, 5A, 5B, 6, 7A, 7B, 8A, 8B, 9A, 9B, 10A, 10B, 11, 12, 13, 14A, 14B, 15, 16, 17, 18, 19, 20	Sum of scores of individual questions divided by number of questions (28).	Missing or not done individual question values will be imputed with the worst possible value (i.e., 4) for summaries
Modified Physical Assessment Subscale	1, 1A, 3, 4A, 4B, 5A, 5B, 6, 9A, 9B, 11, 12, 13, 14A, 14B, 19	Sum of scores of individual questions divided by number of questions (16).	As for Physical Assessment domain
Physical Assessment 5-item Subscale	1, 11, 12, 13, 19	Sum of scores of individual questions divided by number of questions (5).	As for Physical Assessment domain
Physical Assessment 2-item Subscale	1, 12	Sum of scores of individual questions divided by number of questions (2).	As for Physical Assessment domain
Seizure Assessment	23-34	Sum of scores of individual questions divided by number of questions (12).	Missing or not done individual question values will be imputed with the worst possible value for summaries: 1. Questions 23, 25, 26, 27, 29 – 6, 2. Questions 24, 28, 30 – 5, 3. Questions 31, 32 – 3. 4. Question 33 – 2, 5. Question 34 – 1.
Behavioral Assessment (Past Month)	36A, 36B, 37A, 37B, 38A, 38B, 39A, 39B, 40A, 40B, 41A, 41B, 42A, 42B, 43A, 43B, 44A, 44B, 45	Sum of scores of individual questions divided by number of questions (19).	Missing or not done individual question values will be imputed with the worst possible value for summaries: 1. Question 45 – 1, 2. All other questions – 3.
Capability Assessment Given Actual Vision	52-56	Sum of scores of individual questions divided by number of questions (5).	Missing or not done individual question values will be imputed with the worst possible value for summaries: 1. Questions 52-55 – 3, 2. Question 53 – 2.
Clinical Summary	61-67	Each question (including 6 CGIs*** and one assessment of change) will be presented separately.	Missing or not done individual question values will be imputed with the worst possible value for summaries (5).  Question 61 (Assessor's global impression of change since last assessment) value "Not applicable (never seen before)" will not be imputed.

\* NCL history domain of UBDRS (completed by first rater) will be summarized with baseline disease history data

(see details in section [5.7](#)).

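### SAP Table 2 gives worst scores to unscored seizure items 24, 28, 30 and 33 of the UBDRS even when the frequency items show that the seizure type is absent

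*Protocol*

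**What the plan says.** **The form (Protocol Appendix 2).** The header, repeated on later pages, reads "All items must be completed. Use U if information is Unavailable or Not Applicable". One code therefore covers two different situations. Items 24 (tonic/clonic post-ictal period), 28 (complex partial post-ictal period) and 30 (simple partial event duration) each carry the anchor "0 = none/not-applicable". Item 33 (hospitalization for seizures) has "0 = none/not applicable". In the NCL history section the form itself uses U for an absent symptom: "If child has not experienced symptom, code as U for not applicable".

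**The SAP (section 5.2.1, Table 2).** The Seizure Assessment score is the sum of items 23 to 34 divided by 12. For unscored items the rule is "Missing or not done individual question values will be imputed with the worst possible value for summaries", with "Questions 24, 28, 30 – 5" and a value of 2 for item 33. Table 2 does not mention U. It exempts a not-applicable answer from imputation in one place only, Question 61. Observed domain scores and changes from baseline are summarised at each scheduled post-baseline visit.

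**The concern.** A post-ictal period or event duration is undefined for a subject who does not have that seizure type. The form lets the rater record this as 0 or as U. If it is recorded as U, or simply left blank, Table 2 offers only the worst value, and it does not look at the frequency item that would show the question to be inapplicable. The same clinical state could then score 0 or 5 on each of items 24, 28 and 30, and 0 or 2 on item 33.

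The seizure domain is a secondary efficacy result in six subjects with no control arm, so an artefact in one subject is visible in the mean. Coding could also differ between visits. Under Protocol section 7.3.1 the rating is done by live video, with a trained NIH rater if the video fails and a remote assessment if travel is not possible.

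**Working it through.** **Inputs.** Worst values from SAP Table 2, checked against the top anchors on the form:

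| Items | Worst value | Contribution |
|---|---|---|
| 23, 25, 26, 27, 29 (frequency) | 6 | 5 × 6 = 30 |
| 24, 28, 30 (post-ictal period, duration) | 5 | 3 × 5 = 15 |
| 31, 32 | 3 | 2 × 3 = 6 |
| 33 | 2 | 2 |
| 34 | 1 | 1 |

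**The plan's own figures.** Items 23 to 34 make 12 questions, which matches the SAP divisor, and every worst value matches the form. The maximum sum is 30 + 15 + 6 + 2 + 1 = 54, so the maximum domain score is 54/12 = 4.5.

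**Effect of imputing inapplicable items.** The added score is the sum of the imputed values divided by 12. The shift in the group mean from one such subject is that result divided by 6. If not-applicable is scored 0, the addition is 0.

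| Items imputed | Added score | Share of 4.5 | Shift in mean, n = 6 |
|---|---|---|---|
| One of 24, 28, 30 | 5/12 = 0.42 | 9.3% | 0.07 |
| 28 and 30 | 10/12 = 0.83 | 18.5% | 0.14 |
| 24, 28 and 30 | 15/12 = 1.25 | 27.8% | 0.21 |
| 24, 28, 30 and 33 | 17/12 = 1.42 | 31.5% | 0.24 |

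The second row needs no seizure-free subject. It applies to anyone with tonic/clonic but no partial or absence seizures. The last two rows apply in full to a subject with no seizures.

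**Change from baseline.** Coding 0 at baseline and U later on all three items gives a false worsening of 1.25. U followed by 0 gives a false improvement of 1.25. The corresponding figure with item 33 is 1.42.

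**Pairing each item with its frequency item.**
- Items 24 and 30 pair cleanly with items 23 and 29.
- Item 28 does not pair cleanly with item 27. Item 27 also counts absence seizures and item 28 does not, so item 28 can be inapplicable when item 27 is above 0.
- Item 33 covers any seizure type, so all five frequency items (23, 25, 26, 27, 29) must be 0 before it can be set to 0.

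**The case against.** The strongest objection is that the mapping of U is unknown. Table 2 imputes missing or not-done values and never says that U is either. Its one mention of a not-applicable answer excludes that answer from imputation. The SAP is to be read with a CRF that is not available here, and that CRF may differ from the paper form: SAP section 5.7 lists the NCL history answers as yes, no or not done, with no U. This stands, so the figures above are conditional. It does not rescue the rule. An item 24 left blank for any reason is scored 5 even when item 23 is 0.

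It can also be said that a printed anchor for not-applicable should take precedence over a general header, that trained raters would probably enter 0, and that consistent coding yields no false change. This is reasonable, and nothing in the documents shows that raters did use U here. But consistent U still inflates the observed score at every visit, and it can hide a real change. Suppose items 23 and 24 start at 0 and U, and later become 3 and 2. The imputed sum is 0 + 5 = 5 and then 3 + 2 = 5, a change of 0. The true sum rises from 0 to 5, a change of 5/12 = 0.42.

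The endpoint is secondary and descriptive, with no test affected. Item scores are listed, so an artefact could be traced. This limits the severity.

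A reader might infer that item 52 (School) has the same fault, because entry is at 17 or older and a subject may have left school. The documents do not support this. Item 52 has no not-applicable score and so no double coding. Its anchors, up to "3 = unable to attend special needs classroom", can be read as levels of ability and rated after schooling ends. Nor would an artefact there necessarily look like decline: U at both visits gives no change, and U at baseline followed by a lower rating would look like improvement.

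**Conclusion.** The point holds for seizure items 24, 28, 30 and 33. Table 2 assigns the worst value to an unscored item even when other items on the same form show that the question does not apply, and the form's use of U for not-applicable makes such entries more likely. If U is handled as missing or not done, a seizure-free subject can score 1.25 (1.42 with item 33) on a 4.5-point scale instead of 0, and a six-subject mean can move by up to 0.21 (0.24).

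A reader might go further and conclude that the seizure scores are wrong as collected. The documents do not show that. It depends on how the eCRF stores U and on what raters entered. The history-section instruction shows U used for an absent symptom, but that section is neither scored nor imputed. The correction should be made before database lock, but it does not threaten the primary safety objective.

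**What to change.** Amend the Seizure Assessment row of SAP Table 2 before database lock:

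1. If item 24 or item 30 is U, missing or not done and its frequency item (23 or 29 respectively) is 0, score it 0.
2. If item 28 is U, missing or not done, score it 0 when item 27 is 0, or when the subject's record shows that item 27 reflects absence seizures only.
3. If item 33 is U, missing or not done, score it 0 when items 23, 25, 26, 27 and 29 are all 0.
4. Apply worst-value imputation only to seizure items that rules 1 to 3 leave unresolved, and state explicitly how U is mapped.

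These rules use answers already on the form, so they work for ratings already collected, where the two meanings of U can no longer be separated. If the frequency item is itself unscored, the existing rule still applies. The cost is a few lines of SAP text and code, plus a look at the record where item 27 is above 0 and item 28 is unscored. Scoring of the Capability domain need not change on this account.

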#### I. PHYSICAL ASSESSMENT

##### 1. SPEECH CLARITY

1.

0 = normal  
1 = unclear, no need to repeat  
2 = must repeat to be understood  
3 = mostly incomprehensible  
4 = anarthria

##### 1A. ABNORMAL REPETITIVE SPEECH SOUNDS

1A.

0 = none  
1 = sometimes  
2 = most of the time  
3 = constant  
4 = anarthric

##### 2. TONGUE PROTRUSION

2.

0 = maintains full protrusion for 10 seconds  
1 = maintains full protrusion for more than 5 seconds  
2 = maintains full protrusion for less than 5 seconds  
3 = cannot fully protrude tongue  
4 = cannot protrude tongue beyond lips

##### 3. VISUAL ACUITY

3.

0 = normal  
1 = mildly impaired  
2 = finger counting only  
3 = light/dark perception  
4 = blind

##### 4. PASSIVE MOTION-ARMS

Right  Left   
4a.  4b.

0 = normal tone/full range  
1 = mildly increased tone/full range  
2 = moderately increased tone/full range  
3 = markedly increased tone/incomplete range  
4 = minimal or no passive range of motion

##### 5. PASSIVE MOTION-LEGS

Right  Left   
5a.  5b.

0 = normal tone/full range  
1 = mildly increased tone/full range  
2 = moderately increased tone/full range  
3 = markedly increased tone/incomplete range  
4 = minimal or no passive range of motion

##### 6. PASSIVE MOTION-NECK

6.

0 = normal tone/full range  
1 = mildly increased tone/full range  
2 = moderately increased tone/full range  
3 = markedly increased tone/incomplete range  
4 = minimal or no passive range of motion

##### 7. POWER-ARMS

Right  Left   
7a.  7b.

0 = full power  
1 = pronator drift/mild weakness  
2 = moderate weakness/able to actively resist  
3 = severe weakness/able to overcome gravity  
4 = paralysis/unable to overcome gravity

SUBJECT NUMBER 

--	--	--

INITIALS (First, Middle, Last) 

--	--	--

Page 2 of 8  
①

All items must be completed. Use U if information is Unavailable or Not Applicable.

8. POWER-LEGS
 
8a.  Right    8b.  Left
 
0 = full power 1 = mild weakness 2 = moderate weakness/able to actively resist 3 = severe weakness/able to overcome gravity 4 = paralysis/unable to overcome gravity
	
13. RETROPAULSION PULL TEST
 
13. 
 
0 = normal 1 = recovers spontaneously, may take a step back 2 = would fall if not caught 3 = tends to fall spontaneously 4 = cannot stand

9. HAND TAPS (table or thigh)
 
9a.  Right    9b.  Left
 
0 = normal for age 1 = mild slowing and or reduction in amplitude 2 = moderately impaired; definite and early fatiguing; may have occasional arrests in movement 3 = severely impaired; frequent hesitation in initiating movements or arrests in ongoing movements 4 = cannot perform the task
	
14. HEEL STOMPING
 
14a.  Right    14b.  Left
 
0 = normal 1 = mild slowing or reduced amplitude 2 = definite and early fatiguing or occasional arrests in movement 3 = frequent hesitation in initiating movement or arrests in ongoing movement 4 = cannot perform task

10. MAXIMAL DYSTONIA (UPPER EXTREMITIES)
 
10a.  Right    10b.  Left
 
0 = absent 1 = slight/intermittent 2 = mild/persistent or moderate/intermittent 3 = moderate/persistent or marked/intermittent 4 = marked/prolonged
	
15. MOTOR TICS OR STEREOTYPIES
 
15. 
 
0 = absent 1 = rare 2 = mild/common or moderate/intermittent 3 = moderate/common 4 = marked/prolonged

11. NORMAL SPONTANEOUS MOVEMENTS
 
11. 
 
0 = normal 1 = minimally reduced (could be normal) 2 = mildly diminished 3 = moderately diminished 4 = markedly diminished, or absent
	
16. MYOCLONUS
 
16. 
 
0 = absent 1 = rare 2 = mild/common or moderate/intermittent 3 = moderate/common 4 = marked/prolonged


12. GAIT
 
12. 
 
0 = normal gait 1 = small steps and/or slow 2 = walks with difficulty 3 = requires assistance 4 = cannot walk
	
17. REST TREMOR
 
17. 
 
0 = absent 1 = mild amplitude and infrequently present 2 = mild amplitude and usually present 3 = moderate amplitude and usually present 4 = marked amplitude and usually present

SUBJECT NUMBER 

--	--	--

INITIALS (First, Middle, Last) 

--	--	--

**All items must be completed. Use U if information is Unavailable or Not Applicable.**

18. TREMOR WITH MAINTAINED  
POSTURE OR ACTION

18.

0 = absent  
1 = mild amplitude with action  
2 = moderate amplitude with action  
3 = moderate amplitude with action or sustention  
4 = marked amplitude with action or sustention

19. DYSMETRIA (Finger-to-Nose)

19.

0 = normal  
1 = mild irregularity  
2 = moderate irregularity  
3 = marked irregularity  
4 = unable to hit target

20. APPENDICULAR CHOREA

20.

0 = absent  
1 = slight/intermittent  
2 = mild/common or moderate intermittent  
3 = moderate/common  
4 = marked prolonged

21. WEIGHT(lbs.)

21. 

--	--	--

 .

22. MOTOR EXAMINER

22. 

--	--	--

## II. SEIZURE ASSESSMENT

23. GENERALIZED TONIC/CLONIC  
SEIZURES: AVERAGE FREQUENCY

23.

0 = none  
1 = fewer than one per 6 months  
2 = more than one per 6 months and up to one per 3 months  
3 = more than one per 3 months and up to one per month  
4 = more than one per month and up to one per week  
5 = more than one per week and up to one per day  
6 = more than one per day

24. GENERALIZED TONIC/CLONIC  
SEIZURES: POST-ICTAL PERIOD

24.

0 = none/not-applicable  
1 = less than 1 minute  
2 = more than 1 and up to 10 minutes  
3 = more than 10 minutes and up to 1 hour  
4 = more than 1 hour and up to 3 hours  
5 = more than 3 hours

25. ATONIC SEIZURES:  
AVERAGE FREQUENCY

25.

0 = none  
1 = fewer than one per 6 months  
2 = more than one per 6 months and up to one per 3 months  
3 = more than one per 3 months and up to one per month  
4 = more than one per month and up to one per week  
5 = more than one per week and up to one per day  
6 = more than one per day

26. MYOCLONIC SEIZURES:  
AVERAGE FREQUENCY

26.

0 = none  
1 = fewer than one per 6 months  
2 = more than one per 6 months and up to one per 3 months  
3 = more than one per 3 months and up to one per month  
4 = more than one per month and up to one per week  
5 = more than one per week and up to one per day  
6 = more than one per day

SUBJECT NUMBER 

--	--	--

INITIALS (First, Middle, Last) 

--	--	--

Page 4 of 8

(1)

**All items must be completed. Use U if information is Unavailable or Not Applicable.**

27. COMPLEX PARTIAL SEIZURES  
WITHOUT GENERALIZATION  
AND/OR ABSENCE: AVERAGE  
FREQUENCY

27.

3 = more than 10 minutes and up to 1 hour  
4 = more than 1 hour and up to 3 hours  
5 = more than 3 hours

0 = none  
1 = fewer than one per 6 months  
2 = more than one per 6 months and up to one per 3 months  
3 = more than one per 3 months and up to one per month  
4 = more than one per month and up to one per week  
5 = more than one per week and up to one per day  
6 = more than one per day

